4.4. Exclusion period for subjects inclusion in another study if suitable

No exclusion period after the end of the trial participation.

Patients will be excluded for participation in clinical trial investigating the usefulness of IAC during management of acute circulatory failure, but they will be authorized to participate to other studies.

4.5. Study outline

4.6. Schedules of procedures for each enrolled patient

	Inclusion	Short-term follow up until D28 or discharge from ICU (whichever comes first)			Long-term follow up
Study Day 1 starts once patient is randomized		D1, D2, D3	D4, D5, D6, D7	D8 to D28	D90
Inclusion/exclusion criteria	X				
Informed consent	X				
Randomisation	X				
Delayed pursuit consent if applicable		X	X	X	X
Clinical assessment (heart rate, blood pressure, SpO ₂ , pain assessed during transcutaneous vascular puncture ^{a,e} , fluid balance ^b)		X	X	X	
Catheter evaluation (IAC insertion, IAC removal, catheter-related infection)		X	X	X	
Laboratory sampling status (blood volume draw, number of attempts at arterial puncture)		X	X	X	
Therapeutic assessment (number of packs of red blood cells transfused)		X	X	X	
Supportive therapy assessment (respiratory status, ventilator settings ^c , renal replacement therapy ^c , vasopressor support ^b)					
Census evaluation (survival status, in ICU, in Hospital)		X	X	X	X
Specific laboratory testing for the study (SOFA)		X	X		
Blood haemoglobin ^d		X	X	X	
Number of arterial and venous punctures for lab tests, arterial catheter insertion and set up of monitor, blood drawings from arterial catheter or other vascular line, through ICU stay ^e		X	X	X	
Microcosting of staff time and equipment used for arterial and venous punctures for lab tests, arterial catheter insertion and set up of monitor, blood drawings from arterial catheter or other vascular line, through ICU stay ^e		X			
Adverse events/Serious adverse events ^f		X	X	X	X
Query on the French National Hospital Discharge Database (at the end of the study)		X	X	X	

^a: assess by visual or numeric scale for patients able to communicate and by Behavioural Pain Scale(66) otherwise

^b: fluid balance will be assessed only from D1 to D7

^c: if applicable

^d: if available

^e: on a 10% random sample of study population

^f: Collection and reporting of adverse events will begin once the informed consent is signed

Patients' follow-up:

Patients will be examined for signs of shock and organ failures throughout their ICU stay, as done in routine practice.

Their deceased/alive status will be recorded at ICU discharge, hospital discharge, by day 28 and by day 90

Lost-to-follow-up

The study centre personnel will make every possible effort to collect the survival status of the enrolled patients at day 28 and day 90 (by consulting electronic hospital records, telephone contact with family practitioner, or with patient him/herself or relatives).

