4.3. Inclusion and non-inclusion criteria

Inclusion criteria

- Age \geq 18 years the day of inclusion
- Existence of an acute circulatory failure defined by the presence of the following items 1 and 2:
 - 1) Persisting hypotension (systolic blood pressure less than 90 mmHg or mean arterial blood pressure less than 65 mmHg) for more than 15 min at ICU admission or within the following

24 hours, **OR** requirement of continuous iv vasopressor treatment (i.e. any dose of norepinephrine / epinephrine)

- 2) Presence at least one of the following signs of hypoperfusion: alteration of mental status; skin mottling; oliguria defined as a urine output < 0.5 mL/kg body weight for at least one hour; arterial lactate > 2 mmol/L; peripheral venous lactate > 3.2 mmol/L; ScvO₂ <70%
- Free express oral and informed consent of the patient or a proxy in case of impossibility for the patient to consent; emergency inclusion possible when legal representatives and patient's family are not available
- French health insurance holder

Non-inclusion criteria

- Acute circulatory failure, as defined by items 1 and 2 in inclusion criteria list (cf. supra) present for more than 24 hours
- NIBP device fails to display a BP value, or cuff placement impossible
- Patient for whom an ECMO therapy (either veno-arterial or venous-venous) is already in place or is to be initiated within the next 6 hours
- Patient treated with vasopressor doses of more than 2.5 µg/kg/min of *norepinephrine tartrate* plus epinephrine for at least 2 hours (i.e., for instance, more than 8 mg of *norepinephrine tartrate* in 50 mL at the rate of 66 mL/hour for a patient weighing 70 kg) (*please note that in fact this dosage corresponds to 1.25 µg/kg/min of norepinephrine base*)
- Severe traumatic brain injury (i.e., traumatic brain injury with a Glasgow coma scale score of less than 9 before sedation)
- Patient previously included in the trial
- Body mass index (BMI) above 40 kg/m² (33,35,65)
- Pregnancy
- Brain death
- Moribund patient
- Patient known, at time of inclusion, as being under guardianship, tutorship or curatorship

[figure not shown]
N.B.: Note that a patient already carrying an indwelling arterial catheter can still be randomized in the study provided that all the above criteria are respected. If randomised in the “noninvasive group”, the catheter should be removed within one hour following randomisation.

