The study will be conducted in accordance with the present protocol. With the exclusion of emergency situations necessitating taking specific therapeutic actions, the investigator or investigators undertake to observe the protocol in all respects, in particular as regards obtaining consent and the notification and follow-up of serious adverse events.

The study protocol will be submitted to the Ethics Committee (Comité de Protection des Personnes). Data recorded in this study will be participant to computer processing by INSERM CIC-P 1415 – University Hospital Centre of Tours, and these data collected during the trial will be processed in accordance with the requirements of the CNIL (within the framework of the Reference methodology (MR-001) and the General Data Protection Regulation (2016/679- GDPR)).

We intend to present the study as a study exposing enrolled patients to minimal risks and possibly resulting in a favourable benefit/risk ratio for at least one group of patients. If such benefit/risk ratio and study qualification are approved by the CPP, the study protocol will be transmitted to the ANSM for information. Furthermore, if the CPP recognises that the study exposes the patients to minimal risks, we will ask, as allowed by the French Law, to have the possibility to include the patients without prior consent if patient is not able to consent and if relatives or legal representatives are not present. Thereafter, information will be given to the patient and he/she will be asked to give a delayed pursuit-consent if he/she has regained sufficient capacities.

CHRU de Tours, the sponsor of this study, will take out an insurance policy covering third party liability as required by the French Law.

In accordance to the French Law, this research will be registered in the European EudraCT database or in the ANSM “*Recherches et collections biologiques (RCB)*” registry depending on the qualification the CPP gives to the research.

This research will be registered on the web site <http://clinicaltrials.gov/> before the inclusion of the first patient.

^a Loi n° 2012-300 du 5 mars 2012 relative aux recherches impliquant la personne humaine (1) (JORF n°0056 du 6 mars 2012 page 4138)

^b Arrêté du 3 mai 2017 fixant la liste des recherches mentionnées au 2° de l'article L. 1121-1 du code de la santé publique (JORF n°0107 du 6 mai 2017 texte n°30)

Règlement (UE) 2016/679 (RGPD),

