14.2. Study payments

Research subjects will receive no payments or other remuneration for their participation in the study.

15. Evaluation of security

As this research is involving person with minimal risk (non-invasive blood pressure), all serious adverse event, in accordance with regulations in force, have to be reported by the investigator according with each procedure in place for reporting adverse event related to care in the institution. According to the article L1123-10 of the French Public Health Code, in this low risk study (as defined by the article L1121-1), SAEs are not to be declared within 24 hours but are to be collected and registered in the source documents and

The following AEs will be considered SAEs of special interest and are to be recorded in source documents and study CRF, whatever their relation to the study procedures and whatever the study arm the patient is assigned to:

- Ischemia and/or necrosis of finger(s) or toe(s)
- Documented bowel ischemia
- Occurrence or worsening of acute renal failure with need of renal replacement therapy (while there was no need of renal replacement therapy before this event)
- Need of tracheal intubation in a patient previously not intubated
- Cardiac arrest
- Death of any cause

Each adverse event, serious or not, related or not to the study procedure have to be recorded in source documents and study CRF.

For safety purpose, the **following AEs that could potentially be related to the BP measuring method used, will be systematically collected in source documents and study CRF** (not to be declared in real time):

- nerve injury of upper limb(s)
- skin lesions at cuff location or at IAC insertion site
- arterial thrombosis
- hematoma
- arterial pseudo aneurysm
- haemorrhage at IAC insertion site either during IAC placement or later

16. Committees

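### Footnote f ties the start of adverse-event collection to a signed consent, which does not fit emergency inclusions or late signatures, and should be tied to randomisation

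*Protocol*

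**What the plan says.** The only explicit start rule for adverse events is footnote f in Protocol Section 4.6: "Collection and reporting of adverse events will begin once the informed consent is signed". The row it annotates is ticked for every period from D1 to D90. The header of the same table says "Study Day 1 starts once patient is randomized", and Section 4.2 likewise sets H0 at randomisation.

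On consent, Section 4.3 requires "Free express oral and informed consent of the patient or a proxy in case of impossibility for the patient to consent", and allows emergency inclusion when neither family nor a legal representative can be reached. Section 9 describes the request to the ethics committee "to have the possibility to include the patients without prior consent if patient is not able to consent", after which "he/she will be asked to give a delayed pursuit-consent if he/she has regained sufficient capacities". The schedule row "Delayed pursuit consent if applicable" is ticked from D1 to D90.

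On scope, Section 15 says "Each adverse event, serious or not, related or not to the study procedure have to be recorded in source documents and study CRF". It adds that "AEs that could potentially be related to the BP measuring method used, will be systematically collected", and lists six of them. It sets no consent condition and gives no start time.

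On analysis, the SAP keeps every randomised patient apart from those who later object to use of their data or are under guardianship. It compares special-interest adverse events between groups with a chi-squared test.

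**The concern.** For some randomised patients the footnote and its own row give different start times. If a site applied the footnote as written, it would open adverse-event collection at signature, which may be days after randomisation or may never occur.

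The exposed period matters because it holds the contrast between the arms. Section 3 requires the catheter within four hours of randomisation in usual care. Bleeding at the insertion site during placement is one of the events Section 15 lists, and haematoma is another. An early event that was never collected would count as no event, since the SAP keeps the patient in the comparison and its safety section has no rule for a collection period that opened late.

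Fewer catheter complications is a benefit the protocol expects from the new strategy (Section 5), so this comparison needs a common starting point in both arms.

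**Working it through.** The plan gives no figure to reproduce. The check sets the passages side by side and then works out the direction of any error.

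**Step 1. Start of collection by consent route.**

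| Route | Start under footnote f | Start under its row | Agreement |
|---|---|---|---|
| Consent signed before randomisation | At or before randomisation | D1 = randomisation | Yes |
| Oral consent at inclusion, signature after randomisation | At signature | D1 = randomisation | No |
| Oral consent, signature never obtained (if this occurs) | Never | D1 = randomisation | No |
| Emergency inclusion, capacity regained and consent signed | Between D1 and D90 | D1 = randomisation | No, unless signed at once |
| Emergency inclusion, death or no return of capacity | Never, unless someone else signs | D1 = randomisation | No |

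Section 9 makes inclusion without prior consent depend on the ethics committee. Section 4.3 nevertheless lists emergency inclusion as available, and the schedule provides a delayed-consent row.

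**Step 2. Is there another source for the same events?** Section 15 lists six event types possibly related to the measuring method: upper-limb nerve injury, skin lesions, arterial thrombosis, haematoma, pseudoaneurysm and insertion-site haemorrhage. None is named in any schedule row other than the adverse-event row. The catheter row names only insertion, removal and catheter-related infection. So the row governed by footnote f is the only scheduled collection for these six.

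**Step 3. Timing against exposure.** In usual care the catheter is due within 4 hours of H0. A signature later than that can leave the placement period outside a window opened by the footnote. In the non-invasive arm, Section 4.3 has any catheter already in place removed within 1 hour of randomisation, so that arm also has some early exposure.

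**Step 4. Direction.** Let p_U and p_N be the true proportions of patients with at least one special-interest event in usual care and non-invasive care. Let m_U and m_N be the proportions whose only such events fall before collection opens. These patients are counted as event-free, so

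observed difference = (p_U − m_U) − (p_N − m_N) = (p_U − p_N) − (m_U − m_N).

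Catheter harm is understated whenever m_U exceeds m_N. That is the likely case, because systematic insertion takes place in one arm only. It is not certain, because of the early removals in the other arm.

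**Step 5. Size.** To put a value on m_U and m_N one needs the share of patients without a signature at randomisation, the delay to signature, the rate of early events, and how far sites applied the footnote. The documents give none of these. A power figure would rest entirely on assumed inputs, so none is given.

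**Step 6. Primary outcome.** Survival status has its own schedule row and its own follow-up procedure, and footnote f is not attached to it. Day-28 mortality is therefore unaffected.

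**The case against.** The strongest reply is that Section 15 is the full safety text and a table footnote is not. It asks for every adverse event in source documents and CRF, and says the six method-related events need not be declared in real time. On that reading a patient who signs on, say, Day 10 can still have Day 1 events entered from the source documents, and the gap shrinks to patients who never sign. This reading is plausible and largely stands. It is why the point is a risk of uneven collection. It does not remove the point: Section 15 states no start time, the footnote does, and sites may resolve the two differently.

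A second reply is that signed forms are foreseen: Section 10.3 speaks of written agreement for access to data, and Section 12 of archiving signed forms. This also stands. A reader might infer from the oral-consent criterion that some patients enter with no signature at all. The documents make that possible but do not establish it, and the consent pages are not available for review. What remains is that nothing visible requires the signature before randomisation.

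A reader might also infer a conflict with Section 4.10, which bars use of collected data when pursuit-consent is refused. There is none. Many other schedule rows start at D1, so that rule can operate even if no adverse-event data were collected before consent.

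Finally, a patient already carrying a catheter may be randomised, so not every usual-care placement falls after H0. This limits the size of the problem but not the need for a common start.

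**Conclusion.** The inconsistency is real. For emergency inclusions without prior consent, and for any patient included on oral consent whose signature follows randomisation or never comes, footnote f contradicts its own row and does not fit Section 15. For patients who sign before randomisation there is no conflict.

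The consequence depends on a site having followed the footnote literally. If one did, early events could be missing in patients who remain in the SAP's comparison, and the likely effect is to understate catheter harm. A reader might conclude that early safety data were certainly lost. The documents do not support that, because Section 15 points sites towards full recording. The extent cannot be computed from what is given. The point should be corrected and checked, but it does not touch the primary analysis.

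**What to change.** Change footnote f to: *Collection of adverse events begins at randomisation (H0) for every patient, whatever the consent route; data of patients who refuse pursuit-consent are handled as in 4.10.* Cross-refer to it in Section 15. This is one footnote and one cross-reference; sample size, population and endpoints do not change.

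If enrolment has ended, as the SAP's amendment after the December 2024 blind review suggests:

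1. For patients without a signature before randomisation, check from when adverse events were actually collected. Report by arm how many had collection opened late or not at all.
2. If any did, add a sensitivity analysis of special-interest adverse events restricted to patients whose consent was signed before randomisation. The criterion should be the signature, since that is the footnote's trigger; oral consent before randomisation would leave affected patients in the set. Signature before randomisation is a pre-randomisation characteristic, so the arms remain comparable by randomisation within the subset. Do not select on the date or fact of delayed consent, which follows randomisation and depends on recovery.

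The cost is one data query on signature, randomisation and event dates (assuming the CRF holds them), one line in the report and, if needed, one table. Events never entered in the CRF can be recovered only as far as source documents hold them.

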4.7. Measures taken to minimise or avoid bias

Recruitment

All patients admitted in the participating ICUs during the study period will be screened for eligibility. Investigators will make every effort to include all consecutive eligible patients to avoid selection bias. Investigators and study personal at each centre will fill in a screening-log form in which will be recorded included and non included eligible patients' characteristics (age, gender, Simplified Acute Physiology score [SAPS II](67), cause of shock, ICU survival, cause of non inclusion if applicable) to allow assessing the representativeness of the study population and drawing conclusions concerning the generalizability of the results.

Randomisation

Randomisation is mandatory to minimise selection bias.

Stratification

Stratification on centres, invasive mechanical ventilation and vasopressor dosage at time of enrolment is planned to have well balanced groups concerning the general care approach (which could differ between centres).

Definition of safety criteria for IAC insertion in the experimental group

The study scientific committee has set reasonable and consensual safety boundaries that will fix in which circumstances the insertion of an IAC will become an inescapable need. Doing so will contribute to limiting group contamination which would occur if too many patients from the experimental group had an IAC.

Choice of the primary outcome measure

As blinding of investigators and of all ICU staff members is not technically feasible, we chose a "hard" endpoint (Day-28 mortality) to minimise bias.

4.8. Duration of study for each enrolled patient

Patients will be declared included in the study at the time of consent. The intervention period will last 28 days after inclusion. Patients will be followed daily until ICU discharge, until Day 28 for the primary outcome measure (Day 28 mortality), and until Day 90 for mortality (secondary outcome).

The period of follow-up will be extended as needed in case of not resolved serious adverse event.

4.9. Study duration

Duration of the inclusion period: 36 months (given the recruiting capabilities of the participating ICUs)

Duration of each patient's participation: 3 months

Total duration of the study: 39 months

4.10. Rules for interrupting the study

In accordance with the Declaration of Helsinki, patients have the right to withdraw from the study at any time for any reason. The Investigator and Sponsor also have the right to withdraw participants from the study. Patients may be removed from the study for the following reasons: (i) Withdrawal of consent: When a subject withdraws consent before completing the study, the reason for withdrawal of consent is to be documented on the CRF and in source documents. (ii) At the request of the Investigator or Sponsor, whether for administrative or other reasons. In case of adverse event, the specific event and any related test and visit will be recorded on the CRF and the intervention may be stopped if judged necessary for safety reasons. In this instance, the patient will be kept for analysis according to the intention-to-treat principle.

When a subject is removed from the study, all observations collected up to the time of termination will be recorded on the CRF along with the reason for termination, and scheduled safety evaluations and Day 28 follow-up examinations will be conducted, if possible. However, in case of pursuit-consent refusal, the data collected will not be used for statistical analysis and the patient will not be included in the final intention-to-treat analysis.

5. Significance

We estimate the number of ICU patients presenting with shock as defined in our inclusion criteria as at least 25,000/year in France. More than 80% of them probably undergo IAC insertion during ICU stay. On the one hand, we expect several benefits to these patients with the proposed, less invasive intervention: smaller amount of blood drawn for lab tests, less transfusion, and less IAC-related complications such as catheter-related infections. On the other hand, based on recent data, we hypothesize that hemodynamic and ventilatory parameters can be safely monitored without IAC insertion. As a result, we expect that the less invasive strategy, while not affecting mortality (or marginally improving survival, an effect size difficult to capture with the planned sample size), will decrease morbidity through minimizing the burden of catheter-related side effects. This would translate into significant cost savings at hospital and national

6. Sample size and statistical analysis

6.1. Sample size

In a non-inferiority randomised clinical trial, we usually hypothesize *a priori* an equal incidence of the event of interest in the two groups compared. In the present study, our *a priori* hypothesis is different. Indeed, we expect a marginal benefit of the non-invasive approach, because the systematic IAC insertion may harm the patients through catheter-related infections and through blood spoliation. However, even demonstrating that the non-invasive approach is not inferior to the systematic IAC insertion approach could be considered as a positive result (cf., Risk/benefit ratio section).

We therefore assume that the mortality rate at day 28 will be 22.5% in experimental group and 25% in the control group. We set the non-inferiority margin at 5%, power at 80% and alpha risk at 5%. Such hypotheses led us to plan the inclusion of 1010 patients.

